**Table 3: Dose Modification Guidelines for Drug-Related Adverse Events for Pembrolizumab and Epacadostat**

Toxicity	Hold Treatment For Grade	Agent	Timing for Restarting Treatment	Dose Level for	Treatment Discontinuation
Diarrhea/Colitis	2-3	Pembrolizumab	Toxicity resolves to Grade 0-1	n/a	Toxicity does not resolve within 12 weeks of last dose or inability to reduce corticosteroid to 10 mg or less of prednisone or equivalent per day within 12 weeks

		Epacadostat	Toxicity resolves to Grade 0-1	Related: Reduce by 1 dose level Not Related: Same dose level	Toxicity does not resolve within 12 weeks of last dose or inability to reduce corticosteroid to 10 mg or less of prednisone or equivalent per day within 12 weeks
	4	Pembrolizu mab	Permanently discontinue	n/a	Permanently discontinue
		Epacadostat	Permanently discontinue	n/a	Permanently discontinue
AST, ALT, or Increased Bilirubin	2	Pembrolizu mab	Toxicity resolves to Grade 0-1	n/a	Toxicity does not resolve within 12 weeks of
		Epacadostat	Toxicity resolves to Grade 0-1	Related: Reduce by 1 dose level Not Related: Same dose level	Toxicity does not resolve within 12 weeks of last dose
	3-4	Pembrolizu mab	Permanently discontinue	n/a	Permanently discontinue
		Epacadostat	Permanently discontinue	n/a	Permanently discontinue
Type 1 diabetes mellitus (if new onset) or Hyperglycemia	T1DM or 3-4	Pembrolizu mab	Hold pembrolizumab for new onset Type 1 diabetes mellitus or Grade 3-4 hyperglycemia associated with evidence of beta cell failure	n/a	Resume pembrolizumab when subjects are clinically and metabolically stable
		Epacadostat	Toxicity resolves to Grade 0-1	Related: Reduce by 1 dose level Not Related: Same dose level	Resume epacadostat when subjects are clinically and metabolically stable

Dosing interruptions are permitted in the case of medical / surgical events or logistical reasons not related to study therapy (e.g., elective surgery, unrelated medical events, patient vacation, and/or holidays). Subjects should be placed back on study therapy within 3 weeks of the scheduled interruption, unless otherwise discussed with the PI. The reason for interruption should be documented in the patient's study record.

### 5.3.1 Criteria and Procedures for Treatment Interruption

In some circumstances, it may be necessary to temporarily interrupt both study treatments as a result of AEs that may have an unclear relationship to study drug. Any interruptions of > 2 weeks or for LFT abnormalities must be discussed with the medical monitor before resuming

treatment. Treatment with both study drugs should be withheld for drug-related Grade 4 hematologic toxicities, nonhematological toxicity  $\geq$  Grade 3 (including laboratory abnormalities), and severe or life-threatening AEs (see Table 3). Table 3 summarizes the dosing actions for MK-3475 and INCB024360 that must be implemented with the indicated related AEs. Additional information related to dose changes for INCB024360 and MK-3475 can be found in subsequent Sections.

Except in cases of emergency, it is recommended that the investigator consult with the sponsor's medical monitor (or other representative of the sponsor) before temporarily interrupting therapy for reasons other than Protocol-mandated medication hold. Additionally, the investigator must notify the sponsor's medical monitor and study project manager via email before restarting study drug that was temporarily interrupted because of an AE.

Dosing interruptions are permitted in the case of medical / surgical events or logistical reasons not related to study therapy (e.g, elective surgery, unrelated medical events, subject vacation, and/or holidays). Subjects should be placed back on study therapy within 3 weeks of the scheduled interruption, unless otherwise discussed with the sponsor. The reason for interruption should be documented in the subject's study record.

In case toxicity does not resolve to Grade 0 to 1 within 12 weeks after last infusion of MK-3475, study treatment should be discontinued after consultation with the sponsor. With investigator and sponsor agreement, subjects with a laboratory AE still at Grade 2 after 12 weeks may continue treatment in the study only if asymptomatic and controlled. For information on the management of irAEs, see below/next sections.

### **5.3.2 Procedures for Subjects Exhibiting Immune-Related Adverse Events**

This section is meant to apply to suspected irAEs or events of clinical interest (ECIs) of a potential immunologic etiology from INCB024360, MK-3475 or the combination.

Events of clinical interest of a potential immunologic etiology or irAEs may be defined as an AE of unknown etiology, associated with drug exposure and consistent with an immune phenomenon. irAEs may be predicted based on the nature of the MK-3475 or INCB024360 compounds, their mechanism of action, and reported experience with immunotherapies that have a similar mechanism of action. Special attention should be paid to AEs that may be suggestive of potential irAEs. An irAE can occur shortly after the first dose or several months after the last dose of treatment. Of note, the requirement for reporting ECIs applies to all groups, including comparators, of MK-3475.

If an irAE is suspected, efforts should be made to rule out neoplastic, infectious, metabolic, toxin or other etiologic causes before labeling an AE as an irAE. Information on how to identify and evaluate irAEs has been developed and is included in the Event of Clinical Interest and Immune-Related Adverse Event Guidance Document. Subjects who develop a  $\geq$  Grade 2 irAE should be discussed immediately with the PI.

Recommendations for management of specific immune-mediated AEs such as pneumonitis enterocolitis, and hepatitis are detailed in the sections below.

#### **Table 4: General Approach to Handling Immune-Related Adverse Events**

irAE	Withhold/Discontinue Pembrolizumab (MK-3475) and Epacadostat	Supportive Care
Grade 1	No action.	Provide symptomatic treatment.
Grade 2	May withhold MK-3475 and INCB024360. Subjects with intolerable or persistent Grade 2 drug-related AE may hold study medication at physician's discretion. Permanently discontinue study drug for persistent Grade 2 AEs for which treatment with study drug has been held, that do not recover to Grade 0 to 1 within 12 weeks of the last dose.	Consider systemic corticosteroids in addition to appropriate symptomatic treatment.
Grade 3 or severe	Withhold MK-3475 and INCB024360. Discontinue if unable to reduce corticosteroid dose to < 10 mg/day prednisone equivalent within 12 weeks of toxicity or permanently discontinue for any severe or ≥ Grade 3 drug-related AE that recurs or any life-threatening event.  For grade 3 rash, dose interruption and topical treatment (see next column) until resolution are recommended. Resume at same dose although dose reduction in cases of persistent rash can be considered.	Systemic corticosteroids are indicated in addition to appropriate symptomatic treatment.  Topical steroids per physician choice (e.g. hydrocortisone, or stronger). Typically oral steroids are not required.
Grade 4	Permanently discontinue	Systemic corticosteroids are indicated in addition to appropriate symptomatic treatment.

### 5.3.3 Timing of Dose Administration of Epacadostat.

Epacadostat will be administered orally BID every 12 hours without regard to food at the dose identified in this study. If a dose is missed by more than 4 hours, that dose should be skipped and the next dose should be taken at the next scheduled timepoint. All BID doses will be taken in the morning and evening, approximately 12 hours apart.

Subjects will begin treatment with epacadostat on Day 1 of the study and will continue administration through the evening prior to the scheduled date of the subject's post-treatment visit. Subjects should plan to take the AM dose of epacadostat on clinic days also at the same time. There is no priority to the order of administration of epacadostat and pembrolizumab when administered in combination; however, the dose of epacadostat should be taken as close to the regularly scheduled 12-hour dosing interval as possible.

### 5.3.4 Supply, Packaging, and Labeling of Epacadostat

Epacadostat will be available as 25, or 100 mg tablets packaged in high-density polyethylene bottles. All tablet excipients comply with the requirements of the applicable compendial monographs (Ph. Eur., USP/NF) (refer to the iIB). All Incyte investigational

product labels will be in the local language and will comply with the legal requirements of each country.

### **5.3.5 Storage and Dispensing of Epacadostat**

Clinical supplies must be stored as described in the iIB.

An initial bulk supply of epacadostat will be provided to investigative sites prior to enrollment of the first subject. When dispensing to subjects, the investigator or designee will remove the appropriate quantity of epacadostat from their stock, dispense the medication, and enter the amount dispensed into the CRF and drug accountability log.

### **5.3.6 Timing of Dose Administration of Pembrolizumab.**

Combination treatment (during treatment period) should be administered on Day 1 of each cycle after all procedures/assessments have been completed as detailed on the Trial Flow Chart (Section 6.0). Trial treatment may be administered up to 3 days before or after the scheduled Day 1 of each cycle due to administrative reasons.

→ All trial treatments will be administered on an outpatient basis.

Pembrolizumab 200 mg will be administered as a 30-minute IV infusion every 3 weeks until disease progression, unacceptable toxicity, or up to 24 months in patients without disease progression. . Sites should make every effort to target infusion timing to be as close to 30 minutes as possible. However, given the variability of infusion pumps from site to site, a window of -5 minutes and +10 minutes is permitted (i.e., infusion time is 30 minutes: -5 min/+10 min).

The Pharmacy Manual contains specific instructions for the preparation of the pembrolizumab infusion fluid and administration of infusion solution.

### **5.3.7 Trial Blinding/Masking**

This is an open label trial without randomization.

## **5.4 Treatment Allocation**

Please see eligibility / Inclusion criteria for allocation to one of the two cohorts.

## **5.5 Stratification**

There will be no stratification

## **5.6 Concomitant Medications/Vaccinations (allowed & prohibited)**

Medications or vaccinations specifically prohibited in the exclusion criteria are not allowed during the ongoing trial. If there is a clinical indication for one of these or other medications or vaccinations specifically prohibited during the trial, discontinuation from trial therapy or vaccination may be required. The investigator should discuss any questions regarding this with the PI. The final decision on any supportive therapy or vaccination rests with the investigator and/or the subject's primary physician.

### **5.6.1 Acceptable Concomitant Medications**

All treatments that the investigator considers necessary for a subject's welfare may be administered at the discretion of the investigator in keeping with the community standards of medical care.

### **5.6.2 Restricted Medications and Measures**

None, see 5.6.3 prohibited concomitant medications

### **5.6.3 Prohibited Concomitant Medications**

Subjects are prohibited from receiving the following therapies during the Screening and Treatment Phase (including retreatment for post-complete response relapse) of this trial:

- Antineoplastic systemic chemotherapy or biological therapy
- Immunotherapy not specified in this protocol
- Chemotherapy not specified in this protocol
- Investigational agents other than pembrolizumab
- Use of coumarin-based anticoagulants (eg, Coumadin®) is not allowed. Alternatives to coumarin-based anticoagulants should be considered and are acceptable.
- Radiation therapy
  - Note: Radiation therapy to a symptomatic solitary lesion or to the brain may be allowed at the investigator's discretion.
- Live vaccines within 30 days prior to the first dose of trial treatment and while participating in the trial. Examples of live vaccines include, but are not limited to, the following: measles, mumps, rubella, varicella/zoster, yellow fever, rabies, BCG, and typhoid vaccine.
- Systemic glucocorticoids for any purpose other than to modulate symptoms from an event of clinical interest of suspected immunologic etiology. The use of physiologic doses of corticosteroids may be approved after consultation with the PI (typically ≤10mg of Prednisone or equivalent).

- Any melatonin supplements.
- Any MAOI or drug associated with significant MAO inhibitory activity agents is prohibited from 21 days before Day 1 through 2 weeks after the final dose of epacadostat has been taken (see Appendix C).
- Any UGT1A9 inhibitor, including acitretin, amitriptyline, androsterone, cyclosporine, dasatinib, diclofenac, diflunisal, efavirenz, erlotinib, estradiol (17-beta), flutamide, gefitinib, gemfibrozil, glycyrrhetic acid glycyrrhizin, imatinib, imipramine, ketoconazole, linoleic acid, mefenamic acid, mycophenolic acid, niflumic acid, nilotinib, phenobarbital, phenylbutazone, phenytoin, probenecid, propofol, quinidine, ritonavir, Sorafenib, sulfinpyrazone, valproic acid, and verapamil.
- NOTE: Propofol, when used for short-term sedation during surgical/biopsy procedures, is allowed after consultation with the medical monitor. The epacadostat dose may be taken on the morning of the procedure, and the evening dose held following the procedure. Epacadostat may be resumed the next day.

Subjects who, in the assessment by the investigator, require the use of any of the aforementioned treatments for clinical management should be removed from the trial. Subjects may receive other medications that the investigator deems to be medically necessary.

The Exclusion Criteria may describe other medications, which are prohibited in this trial.

There are no prohibited therapies during the Post-Treatment Follow-up Phase.

## **5.7 Rescue Medications & Supportive Care**

### **5.7.1 Supportive Care Guidelines**

Subjects should receive appropriate supportive care measures as deemed necessary by the treating investigator. Suggested supportive care measures for the management of adverse events with potential immunologic etiology are outlined below and in greater detail in the ECI guidance document. Where appropriate, these guidelines include the use of oral or intravenous treatment with corticosteroids as well as additional anti-inflammatory agents if symptoms do not improve with administration of corticosteroids. Note that several courses of steroid tapering may be necessary as symptoms may worsen when the steroid dose is decreased. For each disorder, attempts should be made to rule out other causes such as metastatic disease or bacterial or viral infection, which might require additional supportive care. The treatment guidelines are intended to be applied when the investigator determines the events to be related to pembrolizumab.

Note: if after the evaluation the event is determined not to be related, the investigator is instructed to follow the ECI reporting guidance but does not need to follow the treatment

guidance (as outlined in the ECI guidance document). Refer to Section 5.2.1 for dose modification.

It may be necessary to perform conditional procedures such as bronchoscopy, endoscopy, or skin photography as part of evaluation of the event. Suggested conditional procedures, as appropriate, can be found in the ECI guidance document.

- **Pneumonitis:**

- For **Grade 2 events**, treat with systemic corticosteroids. When symptoms improve to Grade 1 or less, steroid taper should be started and continued over no less than 4 weeks.
- For **Grade 3-4 events**, immediately treat with intravenous steroids. Administer additional anti-inflammatory measures, as needed.
- Add prophylactic antibiotics for opportunistic infections in the case of prolonged steroid administration.

- **Diarrhea/Colitis:**

Subjects should be carefully monitored for signs and symptoms of enterocolitis (such as diarrhea, abdominal pain, blood or mucus in stool, with or without fever) and of bowel perforation (such as peritoneal signs and ileus).

- All subjects who experience diarrhea/colitis should be advised to drink liberal quantities of clear fluids. If sufficient oral fluid intake is not feasible, fluid and electrolytes should be substituted via IV infusion. For Grade 2 or higher diarrhea, consider GI consultation and endoscopy to confirm or rule out colitis.
- For **Grade 2 diarrhea/colitis** that persists greater than 3 days, administer oral corticosteroids.
- For **Grade 3 or 4 diarrhea/colitis** that persists > 1 week, treat with intravenous steroids followed by high dose oral steroids.
- When symptoms improve to Grade 1 or less, steroid taper should be started and continued over no less than 4 weeks.

- **Type 1 diabetes mellitus (if new onset, including diabetic ketoacidosis [DKA]) or ≥ Grade 3 Hyperglycemia, if associated with ketosis (ketonuria) or metabolic acidosis (DKA)**

- For **T1DM** or **Grade 3-4 Hyperglycemia**
  - Insulin replacement therapy is recommended for Type I diabetes mellitus and for Grade 3-4 hyperglycemia associated with metabolic acidosis or ketonuria.
  - Evaluate patients with serum glucose and a metabolic panel, urine ketones, glycosylated hemoglobin, and C-peptide.

- **Hypophysitis:**

- For **Grade 2** events, treat with corticosteroids. When symptoms improve to Grade 1 or less, steroid taper should be started and continued over no less than 4 weeks. Replacement of appropriate hormones may be required as the steroid dose is tapered.
- For **Grade 3-4** events, treat with an initial dose of IV corticosteroids followed by oral corticosteroids. When symptoms improve to Grade 1 or less, steroid taper should be started and continued over no less than 4 weeks. Replacement of appropriate hormones may be required as the steroid dose is tapered.

- **Hyperthyroidism or Hypothyroidism:**

Thyroid disorders can occur at any time during treatment. Monitor patients for changes in thyroid function (at the start of treatment, periodically during treatment, and as indicated based on clinical evaluation) and for clinical signs and symptoms of thyroid disorders.

- **Grade 2** hyperthyroidism events (and **Grade 2-4** hypothyroidism):
  - In hyperthyroidism, non-selective beta-blockers (e.g. propranolol) are suggested as initial therapy.
  - In hypothyroidism, thyroid hormone replacement therapy, with levothyroxine or liothyronine, is indicated per standard of care.
- **Grade 3-4** hyperthyroidism
  - Treat with an initial dose of IV corticosteroid followed by oral corticosteroids. When symptoms improve to Grade 1 or less, steroid taper should be started and continued over no less than 4 weeks. Replacement of appropriate hormones may be required as the steroid dose is tapered.

- **Hepatic:**

- For **Grade 2** events, monitor liver function tests more frequently until returned to baseline values (consider weekly).
  - Treat with IV or oral corticosteroids
- For **Grade 3-4** events, treat with intravenous corticosteroids for 24 to 48 hours.
- When symptoms improve to Grade 1 or less, a steroid taper should be started and continued over no less than 4 weeks.

- **Renal Failure or Nephritis:**

- For **Grade 2** events, treat with corticosteroids.
- For **Grade 3-4** events, treat with systemic corticosteroids.
- When symptoms improve to Grade 1 or less, steroid taper should be started and continued over no less than 4 weeks.

- **Management of Infusion Reactions:** Signs and symptoms usually develop during or shortly after drug infusion and generally resolve completely within 24 hours of completion of infusion.

**Table 5 below shows treatment guidelines for subjects who experience an infusion reaction associated with administration of pembrolizumab (MK-3475).**

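### Section 5.7.1 sets a longer wait before steroids for Grade 3-4 diarrhea/colitis (more than 1 week) than for Grade 2 (more than 3 days), and this conflicts with Table 4

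*Combined protocol and SAP*

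**What the plan says.** Section 5.7.1 has separate bullets by grade for diarrhea/colitis. For Grade 2 the condition and action are "that persists greater than 3 days, administer oral corticosteroids". For Grade 3 or 4 they are "that persists > 1 week, treat with intravenous steroids followed by high dose oral steroids". No earlier steroid instruction is given there for Grade 3 or 4.

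Table 4 in Section 5.3.2 covers immune-related events in general, and its steroid advice rises with grade. At Grade 2 it says "Consider systemic corticosteroids in addition to appropriate symptomatic treatment". In both the Grade 3 and the Grade 4 rows it says "Systemic corticosteroids are indicated in addition to appropriate symptomatic treatment". None of these entries has a persistence condition. The one event-specific exception is at Grade 3: "For grade 3 rash, dose interruption and topical treatment (see next column) until resolution are recommended". Diarrhea/colitis has no exception.

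Section 5.3.2 links the two texts with a pointer: "Recommendations for management of specific immune-mediated AEs such as pneumonitis enterocolitis, and hepatitis are detailed in the sections below". It does not rank them.

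**The concern.** Treatment thresholds would be expected to tighten, or at least not loosen, as severity rises. Here the less severe event reaches its steroid trigger first. The protocol's own grading in Table 8 describes Grade 4 as life-threatening and needing urgent intervention, and Grade 3 as severe enough to indicate hospital admission. A wait of more than a week does not fit either description, and no reason for it is given.

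What is at stake is patient safety. Section 5.7.1 itself asks for monitoring for bowel perforation. Section 4.3.1.3 warns that the combination may produce immune toxicity that is more frequent or more severe than with either drug alone.

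**Working it through.** There is no statistical figure to reproduce. The check is a comparison of the texts.

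**Step 1. The stated thresholds.**

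| Grade of diarrhea/colitis | Section 5.7.1 | Table 4 |
|---|---|---|
| 2 | Oral steroids after more than 3 days | Systemic steroids to be considered; no wait stated |
| 3 or 4 | IV, then high-dose oral steroids, after more than 1 week (7 days) | Systemic steroids indicated; no wait stated |

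**Step 2. Size of the inversion within Section 5.7.1.** The thresholds differ by 7 − 3 = 4 days. Counting whole days from onset (an assumption), the Grade 2 trigger is met from day 4 and the Grade 3-4 trigger from day 8. On days 4 to 7 the section suggests steroids at Grade 2 but not yet at Grade 3-4.

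**Step 3. Difference from Table 4.** If the absence of a stated wait means that steroids are indicated from onset (a further assumption), the two texts differ for Grade 3-4 on days 1 to 7, which is 7 days.

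**Step 4. Is a wait usual in Section 5.7.1?** The event bullets contain these steroid instructions:

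- Grade 2: pneumonitis, diarrhea/colitis, hypophysitis, hepatic, renal = 5.
- Grade 3-4: pneumonitis, diarrhea/colitis, hypophysitis, hyperthyroidism, hepatic, renal = 6.
- Total: 5 + 6 = 11. A wait appears in 2 of the 11, one at each grade level, both for diarrhea/colitis.

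Table 5 (infusion reactions) is left out because it lists corticosteroids as optional and states no wait for them. For contrast, the Grade 3-4 pneumonitis bullet says "immediately treat with intravenous steroids", and the Grade 3-4 hypophysitis bullet says "treat with an initial dose of IV corticosteroids followed by oral corticosteroids".

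**Step 5. Could the wait be time for work-up?** Section 5.7.1 asks that other causes be ruled out, but says its treatment guidelines apply once the investigator judges the event related to pembrolizumab. The wait is therefore not needed to protect the work-up.

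**Step 6. Does another provision set the start of steroids?** The relevant provisions are:

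- Table 3 holds both drugs at Grade 2-3 and stops both at Grade 4.
- Section 5.3.1 withholds both for drug-related non-hematological toxicity of Grade 3 or higher.
- Section 5.3.2 requires immediate discussion with the PI from Grade 2.
- Section 5.7.1 asks for monitoring and fluids, and for GI consultation and endoscopy to be considered from Grade 2.

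None of these says when steroids begin.

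**Step 7. Frequency.** The number of patients affected cannot be derived from the documents. As a rough guide, Section 4.3.1.3 reports Grade 3/4 diarrhea of any cause in 2 of 117 patients at this epacadostat dose (1.7%). If that rate applied here (an assumption), 30 × 2/117 ≈ 0.5 events would be expected in 30 patients.

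**The case against.** The strongest reply has four parts.

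- **Table 4 says that steroids are indicated, not when to start them.** Where the protocol wants immediate treatment it says so, as for pneumonitis. This is fair: the 7-day difference from Table 4 depends on how its silence is read. The inversion within Section 5.7.1 does not depend on it.
- **Table 4 is labelled general and Section 5.3.2 sends the reader onward for enterocolitis, so the specific text arguably governs.** That reading is reasonable, but it would make the inverted rule the operative one.
- **Section 5.7.1 is suggested care, does not forbid earlier steroids, and refers to the ECI guidance document for detail.** All true. That document is not available here, so actual practice cannot be checked and no delay in treatment is shown. Suggested guidance still steers care, and it should not contradict another table in the same protocol.
- **The grade bullets name different regimens, and the right timing is a clinical decision.** The regimens do differ, but that does not explain why the more intensive one should start later. The clinical point does stand as a reason for clinicians to confirm the amended bullet.

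**Conclusion.** The concern holds. The Grade 3-4 trigger is 4 days longer than the Grade 2 trigger, it is the only Grade 3-4 steroid instruction in Section 5.7.1 with a wait, and it conflicts with a general table that attaches no persistence condition. Confidence in the reading of the text is high. The days quoted rest on counting whole days from onset and, for the comparison with Table 4, on taking no stated wait to mean no wait.

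The practical consequence is limited by investigator discretion and the existing safeguards, and the event is probably uncommon. The case for correction rests on severity and on how easy the change is. It should be fixed, but it is not a reason to hold the trial. The primary endpoint, the two-stage design and the sample size are untouched.

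**What to change.** In the Grade 3 or 4 diarrhea/colitis bullet of Section 5.7.1, delete the condition that the event has lasted more than one week, so that steroid timing agrees with Table 4. Table 4 says only that steroids should be systemic, so the responsible clinicians should confirm the route and dose and check the amended bullet against the ECI guidance document.

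The cost is one phrase in one bullet, which can go in the next protocol amendment. It adds no procedures, visits or patients.
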